#### Per Protocol (PP) Analysis Set

The Per Protocol (PP) Analysis Set will be a subset of Safety Set Subjects who have no major protocol violations that exclude them from analyses, and who have a baseline RSA exam and at least one post-baseline RSA exam. Subjects will be analyzed according to the actual treatment (surgical approach) received during of the study.

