#### 8.4 6 Weeks (Day 28-56)

All Subjects will undergo a model-based RSA examination. For all sites, the 6-week exam will be used as the reference examination. RSA radiographs will be obtained with Subjects in a supine position. If not performed earlier, a duplicate RSA exam will be conducted at this time-point to calculate the intra-Subject measurement error.

Additionally, the Subject will have the following health and functional status evaluations:

- Harris Hip Score; ROM optional
- Hip Evaluation
- HOOS Jr.
- Forgotten Joint Score
- Adverse Events (if applicable)
- Radiographs
  - o AP Femur
  - o Lateral

The information collected from the '6 Week' visit will be populated on the appropriate eCRFs as indicated in the Time and Events Table (Section 3.2).

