#### 8.5 3 Month, 6 Month, 1 Year and 2 Year Visits

The Subject will have the following health and functional status evaluations:

4 MAR 2022; Version Rev 3 DSJ-2019-02 Confidential

Page 21 of 47

- Harris Hip Score
- Hip Evaluation
- HOOS Jr.
- Forgotten Joint Score
- Adverse Events (if applicable)
- Radiographs
  - AP Femur
  - o Lateral
- RSA Exam (supine position)

The information collected from these visits will be populated on the appropriate eCRFs as indicated in the Time and Events Table (Section 3.2).

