#### - Time and Events.

2. A Subject returns between study visit intervals

If a Subject requires an additional visit during a study interval, and is seen by one or more persons listed on the Delegation of Authority Log, then the following information shall be repeated:

- Harris Hip Score
- Hip Evaluation
- HOOS Jr.
- Forgotten Joint Score
- Adverse Events (if applicable)

If a Subject has an unscheduled visit after the 6 week interval (outside defined protocol window), with one or more persons listed on the Delegation of Authority Log then the following information shall be collected:

- Harris Hip Score
- Hip Evaluation
- HOOS Jr.
- Forgotten Joint Score

4 MAR 2022; Version Rev 3 DSJ-2019-02 Confidential Page **22** of **47** TV-eFRM-02920

- Adverse Events (if applicable)
- Radiographs
  - o AP Femur
  - o Lateral
- RSA Exam (supine position) if RSA Exam was not conducted in-window for previous visit. If Subject is seen multiple times outside of the same defined protocol window, only one RSA Exam is required.

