#### 8.7 Radiostereometric Analysis (RSA)

The RSA analysis will be the responsibility of the Canadian RSA Network. In summary, model based RSA software (RSAcore, Leiden, Netherlands) will be used for analysis, employing computer-models of the DePuy Synthes implants and inserted beads representing the bone rigid body. A central analysis service will be employed to analyze anonymized radiographs in a standard manner. DePuy Synthes will provide production CAD models as required for this analysis.

Three-dimensional migration measurements will be made of the acetabular shell relative to the bone beads. The 6-week examination will be used as reference against which the 3-month, 6-month, 1-year and 2-year post-operative exams will be compared. Results obtained from the model based RSA software will be changes from the 6-week (baseline) examination and will report the following at 3 months, 6 months, 1 year and 2 years:

- X, Y and Z translation measurements in mm from baseline;
- X, Y and Z rotation measurements in degrees from baseline;
- Maximal total point motion (one measurement in mm of maximal migration).

In a subgroup of Subjects, a second baseline will be defined as the result collected prior to discharge. For these Subjects, the translation, rotation and maximal total point motion will be reported at 6 weeks, 3 months, 6 months, 1 year and 2 years. This sub-analysis will determine the approximate magnitude of migration that occurs between the time of surgery and 6-weeks post-operative. Three-dimensional migration of the PINNACLE® Acetabular Shell shall be determined from the software.

Linear head penetration (in mm) will be performed by examining the change in distance between the center of the femoral head and the center of the acetabular shell between the 6-week (baseline) exam and the 1 year and 2 year exams. The femoral head center is determined by fitting a CAD sphere to the articular region of the femoral head (ignoring the trunnion area). The acetabular shell center is determined in a similar manner but also uses the silhouette of the cup face to determine its' center point.

4 MAR 2022; Version Rev 3 DSJ-2019-02 Confidential

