#### Harris Hip Score at 6 weeks, 3 months, 6 months, 1 year and 2 years

Harris hip scores are assessed at the Pre-Op visit and at 6 weeks, 3 months, 6 months, 1 year and 2 years. Results within each visit window will be summarized and changes from baseline will be provided using the Per Protocol Analysis Set. Standard continuous summaries will be supplemented with 95% confidence intervals. The ROM at 6 weeks is considered optional; the score will be missing for Subjects for whom ROM was not performed.

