#### HOOS Jr. Score at 6 weeks, 3 months, 6 months, 1 year and 2 years

HOOS Jr. Score are assessed at the Pre-Op visit and at 6 weeks, 3 months, 6 months, 1 year and 2 years. Results within each visit window will be summarized and changes from baseline will be provided using the Per Protocol Analysis Set. Standard continuous summaries will be supplemented with 95% confidence intervals.

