#### Forgotten Joint Score (FJS-12)

4 MAR 2022; Version Rev 3 DSJ-2019-02 Confidential Page **30** of **47** 

FJS-12\_are assessed at the 6 week visit and at 3 months, 6 months, 1 year and 2 years. Results within each visit window will be summarized and changes from baseline will be provided using the Per Protocol Analysis Set. Standard continuous summaries will be supplemented with 95% confidence intervals.

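### Post-operative Harris Hip Score, HOOS Jr. and FJS-12 are summarised only in the Per Protocol set, which requires RSA exams the questionnaires do not need; the FJS-12 baseline visit also needs naming.

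*Combined protocol and SAP*

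**What the plan says.** **Analysis sets (11.5).** The Safety Analysis Set is every enrolled subject who has the hip surgery, with no RSA condition. The PP set is the part of it with no excluding major violation and "who have a baseline RSA exam and at least one post-baseline RSA exam".

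**Which exam is baseline.** Section 8.4 states: "For all sites, the 6-week exam will be used as the reference examination". Section 8.7 agrees: "Results obtained from the model based RSA software will be changes from the 6-week (baseline) examination". Section 8.7 also defines a second baseline, the pre-discharge exam, in a subgroup. Section 11.5 does not say whether that one qualifies a subject for PP.

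**Scores (11.12.2).** For the Harris Hip Score: "Results within each visit window will be summarized and changes from baseline will be provided using the Per Protocol Analysis Set". The HOOS Jr. and FJS-12 paragraphs name the same set, and none of the three names another. By contrast, subsidence at every visit is analysed in both PP and the Safety Analysis Set (11.12.1, 11.12.2). Baseline characteristics, including the scores, are tabulated in both sets (11.11). The historical comparison (11.12.4) names no set.

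**FJS-12.** Section 11.12.2 has it "assessed at the 6 week visit and at 3 months, 6 months, 1 year and 2 years", whereas "HOOS Jr. Score are assessed at the Pre-Op visit and at 6 weeks, 3 months, 6 months, 1 year and 2 years". The pre-operative list in 8.1, which is not exhaustive, names the Harris Hip Score and HOOS Jr. but not FJS-12. The synopsis and 5.2 nevertheless place all three scores at baseline, and 11.11 lists FJS-12 among the baseline characteristics.

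**The concern.** Membership of the only set named for the post-operative scores depends on a measurement the scores do not use. A subject can attend, complete every questionnaire and still be absent from the score tables because an RSA exam is missing. Section 11.15 rules out imputation, so nothing else brings those scores back.

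The stake is modest. Some precision is lost on secondary descriptive endpoints whose intervals 11.7 calls exploratory. The reason for omission may also not be random: 10.1 lists adverse events and component revision among the possible reasons for leaving early.

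For FJS-12 the stake is interpretation. An unlabelled change from baseline, tabulated beside two scores that start before surgery, could be read as a change from before surgery. On the schedule as written, it would start at day 28 to 56 after surgery.

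**Working it through.** **1. Who is left out, and of what.**

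| Operated subject, no excluding violation | In PP? | Scores omitted from the specified post-operative summaries |
|---|---|---|
| No qualifying baseline RSA exam | No | All post-operative scores |
| Baseline exam, no later RSA exam | No | Normally the 6-week scores only |
| Baseline exam and at least one later exam | Yes | None |

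The second row says *normally* because 8.5 puts RSA and the questionnaires at the same visits, so a subject with no later RSA exam will usually have no later scores. Even the 6-week loss can be partial. The Harris Hip Score is already missing at 6 weeks where the optional range-of-motion part was not done. If the FJS-12 baseline is 6 weeks, such a subject has no FJS-12 change to lose.

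**2. What limits the first row.**
- The pre-discharge baseline in 8.7 might qualify a subject who missed the 6-week exam; 11.5 is silent.
- Section 8.6 allows, at some unscheduled visits, "RSA Exam (supine position) if RSA Exam was not conducted in-window for previous visit". It does not say whether a late exam can serve as baseline.
- Section 10.2 lets subjects who missed the 6-week visit because of COVID-19 be replaced. That protects the count but does not restore the replaced subject's own scores.

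**3. The plan's own precision figure.** Section 11.8 uses SD 0.2 mm and n = 30: 2 × 0.2/√30 = 0.073 mm, which reproduces. With the t quantile on 29 degrees of freedom it is 0.0747 mm. The figure concerns RSA migration and is not in dispute. The documents give no SD for the scores, so step 4 works in SD units.

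**4. Cost of one lost subject at one visit.** Half-width of a two-sided 95% interval for a mean, in SD units: h(n) = t(0.975, n−1)/√n.

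| Subjects with a score | h before | h after losing one | Ratio |
|---|---|---|---|
| 30 | 0.3734 | 0.3804 (n = 29) | 1.019 |
| 45 | 0.3004 | 0.3040 (n = 44) | 1.012 |

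The starting values 30 and 45 are the enrolment limits in 7.1, and every subject is taken to have a score at the visit. The table shows the smallest possible loss; it does not predict how many subjects will be lost.

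**5. FJS-12 statements side by side.** Sections 8.4, 11.6.2 and 11.12.2 start FJS-12 at 6 weeks, and 8.1 does not list it before surgery. The synopsis and 5.2 speak of a baseline without naming the visit, and 11.11 puts FJS-12 beside scores that are collected pre-operatively. The Time and Events table is not readable in the copy reviewed, so it cannot settle the point.

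**The case against.** The strongest reply is that one cohort for RSA and scores is coherent. The study exists to measure migration, may correlate scores with RSA findings (11.12.3), and tests no hypotheses. Section 11 calls itself a general description, with a fuller SAP to follow. All this stands as a reason to keep the PP tables. It does not explain why the scores lack the supportive Safety Analysis Set summary that subsidence has. Section 11 also says the later SAP will reflect the protocol, which at present names PP only.

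Four stronger readings are tempting, and the documents do not support them.

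- *An appreciable share is lost at every visit.* An assumed 5–20% loss would widen intervals by about 2–13%, but no document figure supports that share. Subjects with no later RSA exam would normally affect only the 6-week visit.
- *The reported scores are biased.* The reasons for leaving make this possible, but neither the number omitted nor how they differ is given.
- *Section 10.2 is contradicted.* It says data received from early discontinuers will enter the analysis, not every table. Those with a later RSA exam stay in PP, and all who were operated on are in the safety and baseline tables. The tension is mild.
- *The FJS-12 change has no valid baseline.* The wording of 11.12.2 points naturally to 6 weeks, and a pre-operative FJS-12 cannot be excluded.

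There is also a fair objection to the remedy. PP has two conditions, and moving to the full Safety Analysis Set drops both, so subjects with excluding major violations would enter the score summaries.

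**Conclusion.** The point holds in limited form. As written, valid post-operative scores are left out of the specified summaries because of missing RSA exams: all of a subject's post-operative scores without a qualifying baseline exam, and normally only the 6-week scores without a later one. The affected group is probably small, and smaller still if the pre-discharge exam counts as a baseline. Each subject lost at a visit costs about 1.9% (from 30) or 1.2% (from 45) in interval width at that visit, assuming an otherwise complete set of scores. No bias figure can be given. The primary endpoint and the sample size are unaffected. The FJS-12 baseline is a real but minor inconsistency of labelling. Both are worth correcting because the correction is nearly free.

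**What to change.** In 11.12.2, keep the PP summaries and add, as supportive, summaries of the three scores in all Safety Analysis Set subjects with a score at the visit; for changes, also require a score at the reference visit. This mirrors the treatment of subsidence. If subjects with major violations are not wanted, apply the PP violation criterion without the RSA-exam criterion. In 11.5, state which RSA exam counts as the qualifying baseline.

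For FJS-12, reconcile the synopsis, 5.2 and 11.11 with 8.1, 8.4, 11.6.2, 11.12.2 and the Time and Events table. If no pre-operative FJS-12 is collected, label the change as change from 6 weeks and remove FJS-12 from the baseline characteristics in 11.11. If one is collected, say so in 8.1 and in the FJS-12 paragraph of 11.12.2.

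The cost is wording in the protocol and SAP before database lock, with no new data. The downsides are a few more tables whose n differs from the RSA tables and, with the full Safety Analysis Set, the inclusion of subjects with major protocol violations.

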#### 11.6 Primary and Secondary Endpoints and Associated Hypotheses

There are no hypotheses associated with the primary or secondary endpoints; endpoints appear below.

#### **11.6.1 Primary Endpoint**

The primary endpoint is the RSA-measured mean superior cup migration (Y translation in mm) at 2 years.

#### **11.6.2** Secondary Endpoints

The secondary endpoints are the following:

- RSA measured subsidence (superior cup migration) at 3 months, 6 months and 1 year.
- Other RSA measurements (X and Z translations in mm, X, Y, and Z rotations in degrees, and maximal total point motion in mm) at all time points
- Linear head penetration at 6 weeks, 1 year and 2 years;
- Harris Hip Score at 6 weeks, 3 months, 6 months, 1 year and 2 years;
- HOOS Jr. at 6 weeks, 3 months, 6 months, 1 year and 2 years;
- Forgotten Joint Score (FJS-12) at 6 weeks, 3 months, 6 months, 1 year and 2 years.

#### **11.6.3 Exploratory Endpoints**

The following will be summarized as exploratory analyses:

4 MAR 2022; Version Rev 3 DSJ-2019-02 Confidential

Page 28 of 47

- Mean subsidence for the subset of Subjects where RSA data was obtained prior to discharge at 6 Weeks, 3 months, 6 months and 1 year and 2 years;
- Correlation of functional and health status outcomes (Harris Hip Score, HOOS Jr, and FJS-12) vs. RSA observations may be explored.
- Incidence of intraprosthetic dislocation (IPD)
- Incidence of intraoperative complications

#### 11.7 Levels of Significance

There are no specific hypotheses being tested in this study. To facilitate clinical interpretation, confidence intervals will accompany primary and secondary endpoint estimates and will be 2-sided 95% confidence intervals; these confidence intervals are considered to be exploratory.

#### 11.8 Sample Size Justification

This study sample size was established to provide adequate precision on the mean subsidence estimate at 2 years. A common standard deviation of 0.2 mm is anticipated. Based upon this standard deviation and a sample size of N=30, a 2-sided 95% confidence interval is anticipated to have a margin of error equal to approximately  $2SE = 2 \times \frac{SD}{\sqrt{n}} = 2 \times \frac{0.2}{\sqrt{30}} = 0.073$  mm. This margin of error was deemed to be an adequate level of precision by the Sponsor.

#### **11.9 General Conventions**

All statistical analysis will be performed using SAS® Version 9.3 or higher, unless otherwise noted. A separate Statistical Analysis Plan (SAP) will provide detail on data derivations and the analyses to be performed for the final study report. It will be approved prior to database lock.

Descriptive statistics for continuous variables will include the number of Subjects with an observation, mean, standard deviation (SD), median, minimum, and maximum. Descriptive statistics for dichotomous/categorical variables will include the count and percentage of Subjects in each category.

Unless specifically stated otherwise, all endpoints will be analyzed by surgical approach and overall, pooling all surgical approaches.

#### 11.10 Disposition of Study Subjects

An overall summary of the number of Subjects in each analysis set (Safety and Per Protocol) who had major protocol deviations, who withdrew before study completion, and who completed the study will be tabulated for all surgical approaches combined.

A patient accounting table to present the number of Subjects in the Safety Analysis Set at each visit interval will be summarized: theoretical due, deaths, withdrawn, and expected due in the interval.

#### 11.11 Demographic and Baseline Characteristics

4 MAR 2022; Version Rev 3 DSJ-2019-02 Confidential

Descriptive statistics summarizing demographics and baseline characteristics will be displayed for both the Safety Analysis Set and the Per Protocol Analysis Set. These summaries will include, but are not limited to, age, gender, BMI, general medical conditions, Harris Hip Score, Hoos Jr. and Forgotten Joint Score.

#### 11.12 Primary, Secondary, and Safety Endpoint Analyses

#### **11.12.1 Primary Endpoint Analysis**

#### RSA Measured Subsidence at 2 years

The primary endpoint of RSA measured subsidence (Y translation, also known as superior cup migration) results in the 2-year visit window will be summarized on the subset of Subjects in the Per Protocol Analysis Set (primary analysis) who have 6 week and 2 year data for the analysis. The analysis will also be conducted on the subset of Subjects in the Safety Analysis Set (supportive analysis) who have 6 week and 2 year data for the analysis. Standard continuous summaries will be provided along with 95% confidence intervals.

#### 11.12.2 Secondary Endpoint Analysis

RSA Measured Subsidence at 3 months, 6 months and 1 year

The analysis for this secondary endpoint will be identical to the analyses described for the primary endpoint except conducted on the results in the 3 month, 6 month, and 1 year visit windows, respectively, using the Per Protocol Analysis Set and the Safety Set.

Linear Head Penetration at 6 weeks, 1 year and 2 years

Linear head penetration will be assessed at 6 weeks, 1 year and 2 years. Results within each visit window will be summarized and changes from baseline will be provided using the Per Protocol Analysis Set.

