	
 
Other RSA measurements (X and Z translations in mm, X, Y, and Z rotations in degrees, and maximal total point motion in mm) at all time points and compare to historical PINNACLE® data
 
Linear head penetration at 6 weeks, 1 year and 2 years and compare to historical PINNACLE® data
 
Functional and health status as measured with Harris Hip Score, HOOS Jr. and Forgotten Joint Score (FJS-12) and compare to historical PINNACLE® data at baseline and 3 months, 6 months and 1 and 2 years post-operative
 

	
 
Exploratory:
 
Subsidence for subset of Subjects where RSA data was obtained prior to discharge and compare to historical PINNACLE® data
 
Analyses to examine the correlation of functional and
 

	
 
health status outcomes vs. RSA observations may be explored
 
Incidence of intraprosthetic dislocation (IPD)
 

	Incidence of intraoperative complications
	
 
The type and frequency of any serious and non-serious device or procedure-related AEs across all study intervals will be summarized
 

Inclusion Criteria	
 
Individuals requiring THA for a severely painful and/or disabled joint (typically due to non-inflammatory degenerative joint disease); failed previous hip surgery; or dislocation risks.
 

	2. Individuals who are able to speak, read and comprehend the informed patient consent document and willing and able to provide informed patient consent for participation in the study and have authorized the transfer of his/her information to DePuy Synthes
	3. Individuals who are willing and able to return for follow-up as specified by the study protocol
	4. Individuals who are a minimum age of 21 years at the time of consent
	
 
Individuals who are willing and able to complete the Subject Hip Outcomes questionnaires as specified by the study protocol
 

Exclusion Criteria	1. Individuals who have an active local or systemic infection

Page 7 of 47

2.	Individuals who have loss of musculature, neuromuscular compromise or vascular deficiency in the affected limb rendering the procedure unjustified.
3.	Individuals with poor bone quality, such as osteoporosis, where, in the surgeon's opinion, there could be considerable migration of the prosthesis or a significant chance of bone fracture and/or the lack of adequate bone to support the implant(s)
4.	Individuals with Charcot's or Paget's disease

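### Does listing 6 weeks as a linear head penetration visit, when 6 weeks is the reference exam, undermine that secondary analysis?

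*Combined protocol and SAP*

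**What the plan says.** Section 8.4 fixes the reference: "For all sites, the 6-week exam will be used as the reference examination". Section 8.7 gives the only definition of linear head penetration. It is the change in distance from the femoral head centre to the "center of the acetabular shell between the 6-week (baseline) exam and the 1 year and 2 year exams". For shell migration, 8.7 uses the same reference: "Results obtained from the model based RSA software will be changes from the 6-week (baseline) examination and will report the following at 3 months", and then the later visits.

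A pre-discharge exam serves as a second baseline in a subgroup. For those subjects "the translation, rotation and maximal total point motion will be reported at 6 weeks, 3 months, 6 months, 1 year and 2 years". Penetration is not on that list.

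The endpoint lists read differently. The synopsis has "Linear head penetration at 6 weeks, 1 year and 2 years and compare to historical" data, 5.2 and 11.6.2 name the same three visits, and the heading in 11.12.2 is "Linear Head Penetration at 6 weeks, 1 year and 2 years". The analysis text under that heading states "Linear head penetration will be assessed at 6 weeks, 1 year and 2 years" and adds: "Results within each visit window will be summarized and changes from baseline will be provided using the Per Protocol Analysis Set". Section 11.12.4 then compares every endpoint with DSJ_2018_02 at the visits where it is assessed.

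**The concern.** A change measured from the 6-week exam has no informative value at 6 weeks. Read literally, the endpoint lists ask for a summary, and perhaps a t-test against the historical study, of a quantity that 8.7 does not define at that visit. The plan seems to handle the same reference properly for subsidence: the listed outcome visits start at 3 months, and 6-week subsidence appears only in the subset with a pre-discharge exam. That contrast makes the 6-week penetration entry look like an error.

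Two further doubts follow. If the per-visit result is already a change, asking for change from baseline as well looks like subtracting twice. If it is a raw distance, it is not penetration, and 11.12.4 does not say which of the two is compared with the historical data.

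The Forgotten Joint Score (FJS-12) raises a related question. The synopsis, 5.2 and 11.11 refer to a baseline score. Sections 11.6.2 and 11.12.2 start the score at 6 weeks, yet 11.12.2 still asks for change from a baseline that it does not name.

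At stake would be a meaningless row in a secondary table, two programmers producing different tables, or a historical comparison of the wrong quantity.

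**Working it through.** **The plan's own figure.** The only precision figure is the margin of error in 11.8: 2 × 0.2/√30 = 0.4/5.477 = 0.073 mm, which reproduces. Its inputs are the SD of 2-year subsidence and N = 30. Head penetration does not enter it.

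**Count of the mismatch.** Six weeks is named as a penetration visit in the synopsis, 5.2, 11.6.2, and both the heading and text of 11.12.2: five mentions in four sections. Section 8.7 defines penetration at 1 year and 2 years, two of the three listed visits.

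**Does the reading change the result?** Let d(t) be the head-to-shell centre distance at visit t.

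- Reading A, where the per-visit result is the distance. The table shows d(6 wk), d(1 y) and d(2 y). The changes from baseline are d(1 y) − d(6 wk) and d(2 y) − d(6 wk).
- Reading B, where the per-visit result is penetration as 8.7 defines it, p(t) = d(t) − d(6 wk). Then p(6 wk) = d(6 wk) − d(6 wk) = 0, p(1 y) = d(1 y) − d(6 wk) and p(2 y) = d(2 y) − d(6 wk). A further change from baseline is p(t) − p(6 wk) = p(t) − 0 = p(t).

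The changes at 1 year and 2 years are the same under both readings. Subtracting twice does no harm, because the second subtraction removes zero. The readings differ only in the per-visit rows, and at 6 weeks that row is either d(6 wk) or 0.

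**Which reading does the text support?** The Harris Hip Score and HOOS Jr. paragraphs in 11.12.2 follow one pattern: name the assessed visits including the baseline (Pre-Op), summarise each window, then give changes from baseline. The penetration paragraph fits that pattern with 6 weeks as the baseline, which is what 8.7 calls it. A 6-week reading is needed before any change can be calculated.

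**Is the visit list unusually loose?** No. The synopsis sample-size entry says mean subsidence is summarised at every time point, and the other RSA measurements are listed the same way, although 8.7 reports migration from 3 months. Visit lists are loose across the RSA endpoints, and 8.7 supplies the working definition.

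**FJS-12.** Take 6 weeks as its baseline. The synopsis and 5.2 then give baseline plus 3 months, 6 months, 1 year and 2 years, which is five visits. Section 11.6.2 gives 6 weeks plus the same four, also five. A change exists at four of the five. Section 8.1 does not list the score before surgery and 8.4 lists it at 6 weeks, which agrees. Section 11.11 does not say that its baseline summaries are all pre-operative.

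**The case for a change.** The strongest reply is that an endpoint list should not name a visit at which the endpoint has no value. The wording departs from 8.7 in four sections, and nothing else supplies a 6-week value, since the second baseline leaves penetration out. Section 11.12.4 could then be taken to require a 6-week comparison, without saying whether distance or change is compared. As a point about wording, this stands.

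The harms drawn from it are weaker:

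- An undefined 0/0 t-test at 6 weeks requires someone to subtract the reference from itself. It also requires DSJ_2018_02 to use the same reference exam, which these documents do not state. Such a row would be visibly empty and could not mislead.
- A raw-distance contrast driven by differences between the constructs is possible, but the documents give no distances and no historical penetration data, so it cannot be sized. The endpoint named for comparison is penetration, which 8.7 defines as a change.
- On FJS-12, the synopsis and 5.2 sentence covers three instruments at once and may be shorthand, and the list in 8.1 is not exhaustive. The Time and Events table was not legible in the text available to me, so a pre-operative score cannot be ruled out. That leaves a baseline visit to be named, not a demonstrated error.

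**Conclusion.** The inconsistency is genuine and clerical. Followed as written, with 8.7 as the definition, the plan gives sound 1-year and 2-year penetration changes and a sound basis for comparing them with the historical study. What is left over is one 6-week row, either zero or a reference distance, in a secondary table. The primary endpoint and the 0.073 mm margin do not involve it.

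Sections 11.6 and 11.7 state that no hypotheses are tested, and 11.12.4 offers its p-values only as an aid to clinical judgement. Sections 11 and 11.9 leave derivations to a separate SAP, to be approved before database lock. That is where an analyst would ordinarily record 6 weeks as the penetration reference and name the FJS-12 baseline visit.

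This conclusion assumes that 8.7 governs the meaning of penetration and that the analyst compares the change, not the raw distance, under 11.12.4. Whether DSJ_2018_02 uses the same reference exam is not stated, and removing 6 weeks from four visit lists would not settle that. A wording change would tidy the text but alter no result or conclusion.
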